7.4 SCREENING ASSESSMENTS

Toxicities which occur prior to the start of treatment will not be subject to analysis. Consent must be obtained before initiation of any clinical screening procedure that is performed solely for the purpose of determining eligibility for this research study. Evaluations performed as part of routine care before informed consent can be utilized as screening evaluations if done within the defined time period.

Screening assessments will occur over a 28-day period prior to start of treatment with study agent. Participants will be evaluated for medical history, physical examination, vital signs, ECOG performance status, chest X-ray, concomitant medications, blood sampling for laboratory tests, ECG evaluation, bone marrow biopsy aspiration/biopsy.

Ex vivo sensitivity analysis of AML cells from either bone marrow aspirate or peripheral blood will be completed no later than 7 days prior to initiating treatment. Peripheral blood may be used in place of bone marrow if participant cannot be aspirated or patient has undergone bone marrow biopsy within the last 10 days prior to desired screening date and blast cells comprise $\geq 20\%$ of circulating nucleated cells.

7.4.1 INFORMATION TO BE COLLECTED ON SCREENING FAILURES

A participant who signed an informed consent form but failed to be started on treatment for any reason will be considered a screen failure. Those found not to be eligible after signing the main study consent will be considered screening failures, and data will be handled in the same manner. The demographic information and informed consent. No other data will be entered into the clinical database for individuals who are screen failures.

7.5 ASSESSMENTS DURING TREATMENT

Visits will occur on Day 1 of every cycle. Additional visits in cycles 1 and 2 are listed in the schedule of assessments. Under certain circumstances (e.g., clinic holiday, inclement weather) Day 1 may be delayed by not more than 3 days, or occur earlier than scheduled by not more than 3 days during Cycle 2 and subsequent cycles. Specific on-study assessments are listed in the Section 7.10, Schedule of Events .

Initial response to JNJ-40346527 will be assessed by bone marrow biopsy after cycles 1-3 and every 3 months thereafter. Tumor response will be evaluated per International Working Group (IWG) criteria for AML (refer to Section 8). All studies must be obtained ± 7 day of stated time point.

7.6 END OF TREATMENT VISIT

Participants will be followed until death. Participants will be evaluated for end of treatment within \pm 7 days after stopping JNJ-40346527. End of treatment assessments are listed in the Section 7.10, Schedule of Events . If participants do not reach the end of treatment due to transition to hospice or death, an end of treatment visit will not be conducted.

7.7 FOLLOW-UP

Participants will be followed every 6 months until death. Participants removed from protocol therapy for unacceptable AE(s) will be followed until resolution or stabilization of the AE.

7.8 EARLY TERMINATION VISIT

Study assessments for an early termination visit will mirror the end of treatment visit. A standard of care treatment plan will be formulated as soon as possible for those participants that withdraw from the study abruptly for any reason. Participants will be encouraged to return for the follow-up visit.

7.9 UNSCHEDULED VISITS

Section 7.10, Schedule of Events lists the mandatory data collected at each time point for the clinical trial but it is expected that additional tests/procedures or visits may occur as standard of care, which is entirely at the discretion of the investigator. Most participants will have additional laboratory studies and clinical evaluations outside of this schedule as part of their standard of care. The labs or studies outlined in the schedule of events may be completed within 7 days of the target week (i.e., 7 days before or 7 days after). Every effort will be made to adhere to this schedule as close as possible. This is the minimum schedule of laboratory studies and follow-up visits required for the study.

7.10 SCHEDULE OF EVENTS

Ex vivo screening	X		X	X		X			
FACS	X			X		X			
RNAseq	X	X		X		X			
Research Blood Samples ^K	X	X	X	X	X	X	X	X	

* In general, assessments/procedures are to be performed on Day 1 and prior to the first dose of treatment for each cycle unless otherwise specified. Treatment cycles are 28 days; however the treatment cycle interval may be increased due to toxicity according to the dose modification guidelines provided in Section 6.2.. If the interval is increased, all procedures except imaging should be performed based on the new dosing schedule.

** In general, the window for each visit is \pm 7 days unless otherwise noted.

*** Point of care CBC will be run every 2 weeks during Cycle 2. Once a cycle in subsequent cycles (Cycle 3+).

† Study treatment will end upon evidence of disease progression as defined by IWG for AML. Refer to Section 8 for additional details.

‡ Participants will be followed until death. Participants may be contacted by phone, and survival status will be collected and documented

^ JNJ-40346527 (150 mg) is administered PO twice daily.

B For concomitant medications – enter new medications started during the trial through the EOT visit. Record all medications taken for grade 3 and 4 SAEs as defined in Section 9.6.

C Full physical exam at screening visit. Direct physical exam for all other visits. All physical exams will include assessing weight, vital signs, and ECOG performance status. Height will be measured at screening visit only.

D Chest X-ray at screening will be performed within 28 days prior to the first dose of trial treatment. Scans performed as part of routine clinical management are acceptable for use as the screening image if they are of diagnostic quality and performed within 28 days prior to the first dose of trial treatment.

E After Cycle 1, pre-dose lab samples can be collected up to 72 hours prior to the scheduled time point. Hematology and biochemistry tests should be collected pre-dose on Day 1 of every 28 day cycle. Testing for HCV B or C will only take place during screening.

F For women of reproductive potential, a urine pregnancy test should be performed within 14 days prior to first dose of trial treatment. If urine pregnancy results cannot be confirmed as negative, a serum pregnancy test performed by the local study site laboratory will be required. Pregnancy tests (serum and/or urine tests) should be repeated, if required, per institutional guidelines.

G Peripheral blood may be used in place of bone marrow and blast cells comprise \geq 20% of circulating nucleated cells.

H Standard of care bone marrow exams are done at screening and Day 29 for Cycles 1-3, and every 3 months for subsequent cycles.

I Skin punch biopsy will be collected once anytime during the study.

J AEs and laboratory safety measurements will be graded per NCI CTCAE version 5.0. All AEs, whether gradable by CTCAE or not, will also be evaluated for seriousness. Record grade 3 and 4 AEs occurring within 30 days after the last dose of trial treatment. Report grade 3 and 4 hem and non-hem SAEs (related and unrelated to trial treatment) occurring up until 90 days after the last dose of trial treatment, or the start of new anti-cancer treatment, whichever comes first. Afterwards, report only SAEs that are related to trial treatment.

K Research blood samples will be drawn during standard of care lab draw.

8. EFFICACY MEASURES

8.1 DEFINITION OF EFFICACY MEASURES

Assessment of clinical response will be made according to IWG criteria.²⁰ The major criteria for judging response will include physical examination and examination of blood and bone marrow. Relevant laboratory studies that are abnormal prior to study will be repeated according to the study schedule to document the degree of maximal response.

8.1.1 EVALUABLE FOR TOXICITY

All participants who have received at least 1 dose of study agent will be evaluable for toxicity from the time of their first treatment with JNJ-40346527.

8.1.2 EVALUABLE FOR OBJECTIVE RESPONSE

Only those participants who have completed at least 1 cycle of study agent will be evaluable.

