Exploratory Objectives	
1. Evaluate the pharmacokinetics of JNJ-40346527 and effective inhibition of CSF-1R in marrow aspirates using plasma inhibitory assays with established CSF-1R-sensitive cell lines.2. Identify the effect of JNJ-40346527 on leukemia cells and the immune microenvironment.3. Analyze the frequency of mutations using genomic DNA from leukemia participants to determine if there is a genetic signature that predicts response to JNJ-40346527.4. Using RNA sequencing (RNAseq), identify an expression signature in CSF-1R⁺ cells that predicts patient response.5. Evaluate the effect of JNJ-40346527 on immune cell populations (cytotoxic T cells, etc.) and phospho-signaling proteins by CyTOF analysis in pre- and post-treatment samples in order to identify biomarkers that predict patient response and prioritize potential combination strategies for future clinical trials.6. Determine how leukemia cells change in response to CSF-1R inhibition by assessing cells collected pre- and post-treatment using an ex vivo sensitivity to a panel of small molecule inhibitors to determine what new drug sensitivities may emerge in AML cells after CSF-1R inhibition.
Number of Participants	Up to 28 participants (14 in each arm) will be enrolled. There will be 7 patients in Stage I and 7 patients in Stage II with the total of 14 patients per arm. Given the expected accrual rate of 14 participants per year, the study is expected to take 36 months (24 months of accrual period and the minimum follow-up of 12 months).
Duration of Therapy	Participants demonstrating favorable response to treatment are eligible to continue additional cycles of study agent until disease progression, death, or investigator discretion.
Duration of Follow Up	Until death or minimum of 12 months follow-up from the last dose of JNJ-40346527.
Inclusion Criteria	
1. Ability to understand and the willingness to sign a written informed consent document.2. Age ≥ 18 years at time of informed consent. Both men and women and members of all races and ethnic groups will be included.3. Morphologically documented relapsed/refractory AML as defined by World Health organization (WHO) criteria after at least 1 prior therapy for AML with the exception of hydroxyurea, and not felt to have curative treatment options per treating physician, or the patients themselves are unwilling to consider curative treatment options.

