4.6.1 HANDLING PARTICIPANT WITHDRAWAL AND DISCONTINUATION

Participants that discontinue the first cycle without experiencing a DLT may be replaced. Participants may be replaced if they voluntarily withdraw from the protocol, or if the participant is taken off study per the PI's discretion for reasons such as continued noncompliance. Per 45 CFR 46, the reasons for withdrawal, if known, will be recorded.

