4.7.1 SCREEN FAILURE

Any participant that has signed the consent form (for either screening or study participation) but does not meet the study eligibility criteria, or meets study eligibility criteria but terminates the participation prior to receiving study treatment, will be considered a screen failure. The reason for screen failure should be captured in the database for each participant failing to meet the eligibility criteria.

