10.1 ANALYSIS POPULATIONS

Most common analysis populations are described below:

Analysis Population	Definition	Endpoint
Intent to Treat (ITT)	Those who consent and are registered for the trial regardless of actual receipt of screening or treatment	Used to report accrual
Evaluable for Safety	Those who received at least one dose of JNJ 40346527	Incidence of DLT and SAE
Evaluable for Response	Those who received at least one cycle of JNJ 40346527 and have response measurements	Best objective response
Evaluable for Overall Survival and Event-Free Survival	Those who received at least one dose of JNJ 40346527 and have survival information	Overall survival

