10.4 HANDLING OF MISSING DATA

Missing data will not be imputed. Whenever possible, the analysis will be conducted using all available data. Missing data will be reported in the descriptive summary, and it will be noted if some subjects are excluded from the analysis due to missing data.

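### The primary response rate omits dosed participants who stop in cycle 1, and the 1-of-7 and 3-of-14 rules have no defined denominator when that happens

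*Combined protocol and SAP*

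**What the plan says.** Two sections of the combined protocol and SAP set the response population. Section 8.1.2: "Only those participants who have completed at least 1 cycle of study agent will be evaluable". Section 10.1, for best objective response: "Those who received at least one cycle of JNJ 40346527 and have response measurements". The ITT set in the same table has a single purpose, "Used to report accrual", and Section 10.4 adds "Missing data will not be imputed", with exclusions for missing data to be noted.

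The Simon counts carry three descriptions. The Synopsis ("Up to 28 participants (14 in each arm) will be enrolled"), Section 3.1 and Section 10.2.1 speak of enrolled patients. Section 3.1 also calls the 7 eligible participants. Section 10.2.4 ties the futility look to the first 7 once they have had two cycles.

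On replacement, Section 4.6.1 says "Participants that discontinue the first cycle without experiencing a DLT may be replaced". Its next sentence also permits replacement after voluntary withdrawal or removal at the PI's discretion, without mentioning DLT. Participants who never receive drug are screen failures: Section 4.7.1 covers anyone eligible who "terminates the participation prior to receiving study treatment, will be considered a screen failure", and Section 7.4.1 anyone who "failed to be started on treatment for any reason will be considered a screen failure".

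**The concern.** The first scheduled on-treatment marrow is Cycle 1 Day 29 (Section 7.2.5). A dosed participant who dies, withdraws, deteriorates, or has progression shown on an unscheduled marrow before then is left out of the primary rate, and no other planned response analysis brings that participant back. Most such participants would be expected to be non-responders, so leaving them out raises the rate as a description of treated patients.

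The decision rule has a related gap. Because undosed participants are screen failures, the open question is whether 7 and 14 count treated or response-evaluable patients. Replacement is optional, is not tied to those counts, and is not reconciled with the maximum of 28. Suppose one of 14 treated participants stops in week 2. Two statisticians could then apply the 3-of-14 rule differently to the same data. In an arm of 14, one or two patients can change the conclusion.

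**Working it through.** **Inputs.** Null rate 5%, target 30%, one-sided 5% level, 80% power (Synopsis; Section 10.3.1). Stage 1 has 7 per arm and continues with at least 1 response; the arm is promising with at least 3 of 14 (Section 10.2.1). The cap is 14 per arm, 28 in total (Synopsis). The share e of dosed participants who stop in cycle 1 is not given; I assume 10-40%.

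**1. The stated design reproduces.** P(promising) = Σ over x = 1 to 7 of P(X1 = x) × P(X2 ≥ max(0, 3 − x)), with X1 and X2 each binomial(7, p).
- p = 0.05: 0.2573 × 0.0444 + 0.0406 × 0.3017 + 0.0038 = 0.027.
- p = 0.30: 0.2471 × 0.6706 + 0.3177 × 0.9176 + 0.3529 = 0.810.

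**2. Effect on the estimate.** Three responders among 14 treated are 3/14 = 21.4% (exact 95% CI 4.7 to 50.8%). If 4 stoppers are dropped, the same data read 3/10 = 30.0% (6.7 to 65.2%). In general, if all stoppers are non-responders, a true all-treated rate of 5% appears as 0.05/(1 − e). The chance that at least one of 14 is omitted is 1 − (1 − e)^14.

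| e | True 5% appears as | At least one of 14 omitted | Treated needed for 14 evaluable, 14/(1 − e) | P(promising) at true 5%, full replacement |
|---|---|---|---|---|
| 10% | 5.6% | 77% | 15.6 | 0.036 |
| 20% | 6.3% | 96% | 17.5 | 0.048 |
| 30% | 7.1% | 99% | 20.0 | 0.067 |
| 40% | 8.3% | over 99% | 23.3 | 0.097 |

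The last column puts p = 0.05/(1 − e) into the formula of step 1. It reaches 0.05 at an evaluable rate of 0.0633, that is at e = 1 − 0.05/0.0633 = 0.21.

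**3. Decision error within the cap.** With at most 14 treated, no replacement beyond them and the bar kept at 3, the error at a true all-treated 5% cannot exceed P(X ≥ 3 | 14, 0.05) = 0.030, wherever the stage 1 look falls. With the look at the first 7 treated it is 0.027.

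**4. If the rates are meant for evaluable patients.** When 14 evaluable are reached, 0.027 and 0.81 hold. When stoppers are neither counted nor replaced and the bar stays at 3, power at a 30% evaluable rate depends on when the losses occur:

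| Evaluable, stage 1 + stage 2 | Power |
|---|---|
| 7 + 6 = 13 | 0.78 |
| 7 + 5 = 12 | 0.73 |
| 6 + 6 = 12 | 0.72 |
| 7 + 4 = 11 | 0.68 |
| 5 + 6 = 11 | 0.64 |

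**5. If all 14 treated are counted but 30% was meant for evaluable patients.** The all-treated rate is 0.30(1 − e), and power is 0.74, 0.66 and 0.56 at e = 10, 20 and 30%.

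**The case against.** Response-evaluable sets are common in phase 2. This one has a pharmacological rationale, since steady state is reached at about 21 days (Section 1.3.3.1), and the stated aim is only preliminary efficacy. Early failures are not hidden: all dosed participants stay in the safety set, those with survival information stay in the survival set, and Section 10.4 promises to note exclusions. A reader could rebuild an all-treated rate. These points limit the harm, but they do not say what 7 and 14 count.

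Counting every stopper as a non-responder is not neutral either. If half of the early stops are unrelated to outcome, a true 5% appears under the current plan as 0.05/(1 − 0.5e), that is 5.3, 5.6, 5.9 and 6.3% at e = 10, 20, 30 and 40%. With all stoppers counted as failures it appears as 0.05(1 − e)/(1 − 0.5e), that is 4.7, 4.4, 4.1 and 3.75%. The bias has the same size in the other direction. This objection stands, and it is why the evaluable set should be kept as a sensitivity analysis.

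Three stronger readings are tempting but not supported:
- **Progressors in general leave the denominator.** A participant found progressing at Day 29 has completed a cycle, and Section 10.2.1 lists progressive disease as a category. Only earlier losses drop out.
- **A participant who stops for a DLT can never be replaced.** The second sentence of Section 4.6.1 has no DLT exclusion and could cover some of them.
- **The false-positive rate rises to 7-10%.** That needs full replacement beyond the cap, e above about 21%, every stopper a non-responder, and a 5% null defined for all treated. Section 10.3.1 does not say which population the 5% describes.

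**Conclusion.** The concern holds as a problem of denominator definition. The sample-size arithmetic is correct. As an estimate for treated patients, the primary rate is biased upward whenever early stoppers are mostly non-responders. Over the assumed e of 10-40%, with all stoppers non-responders, the shift is 0.6 to 3.3 percentage points on a true 5%. The 1-of-7 and 3-of-14 rules are undefined once anyone stops in cycle 1, and at e of 10% or more the chance of at least one such stop among 14 treated is 77% or higher.

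The documents do not show an inflated type I error: within 14 treated per arm it is at most 3.0%. The more likely cost is lost power if stoppers are neither counted nor replaced. Confidence is high on the gap in the text. The sizes rest on an assumed e.

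**What to change.** - **Sections 8.1.2 and 10.1:** define the primary response set as all participants who received at least one dose, by assigned arm. Count those without a qualifying response assessment as non-responders at both the stage 1 and the final decision.
- **Sections 3.1, 10.2.1, 10.2.4 and 10.3.1:** state that 7, 14, 5% and 30% all refer to this set, and that the two-cycle wording sets only the timing of the look.
- **Section 4.6.1:** state that dosed participants are not replaced in the primary response analysis.
- **Sensitivity analysis:** keep the completed-one-cycle set, labelled as such.

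No visits or procedures are added, but there is a cost. The reported rate will be lower, and conservative if some early stops are unrelated to outcome. The sponsor must also decide what the 30% means. As an all-treated target it keeps 14 per arm and power 0.81, but implies a completer rate of 0.30/(1 − e), or 33 to 43% at e = 10 to 30%. If 30% was meant for evaluable patients, the protocol should restate power with 14 treated as 0.74, 0.66 or 0.56 at e = 10, 20 or 30%.

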8.2 RESPONSE CRITERIA FOR AML

The objective response rate will be defined as \geq PR, including cytogenetic and molecular responses when applicable, and will be determined at the end of each cycle.

Complete Remission (CR)*:

- Bone marrow blasts < 5%;
- Absence of blasts with Auer rods;
- Absence of extramedullary disease;
- Absolute neutrophil count $>1 \times 10^9/L$ (1000/ μ L);
- Platelet count $> 100 \times 10^9/L$ (100,000/ μ L);
- Independence of red cell transfusions

Morphologic CR:

- Bone marrow blasts <5%;
- Absence of blasts with Auer rods;
- Absence of extramedullary disease;
- No hematologic recovery required

Partial Remission

- Relevant in the setting of phase 1 and 2 clinical trials only;
- All hematologic criteria of CR;
- Decrease of bone marrow blast percentage to 5% to 25%;
- Decrease of pretreatment bone marrow blast percentage by at least 50%

Cytogenetic Complete Remission (CRc):

- Reversion to a normal karyotype at the time of morphologic CR in cases with an abnormal karyotype at the time of diagnosis; based on the evaluation of 20 metaphase cells from bone marrow.

Molecular CR (CRm):

- Molecular studies are negative (i.e., normal molecular markers in persons with previously abnormal molecular studies (e.g. c-KIT, NPM1, FLT3).

CR with incomplete recovery (CRI): • All CR criteria except for residual neutropenia ($< 1 \times 10^9/L$ [$1000/\mu L$]), or thrombocytopenia ($< 100 \times 10^9/L$ [$100,000/\mu L$]).

Stable disease (SD) Not fulfilling either PR or PD criteria and clinical stability

Progressive disease (PD) Increase in blasts by $\geq 50\%$

Definitions of response criteria are amended from Cheson et al.²⁰

*All criteria need to be fulfilled; marrow evaluation should be based on a count of 200 nucleated cells in an aspirate with spicules; if ambiguous, consider repeat exam after 5 to 7 days; flow cytometric evaluation may help to distinguish between persistent leukemia and regenerating normal marrow; a marrow biopsy should be performed in cases of dry tap, or if no spicules are obtained; no minimum duration of response required.

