6.3 TREATMENT PERIOD AND MAINTENANCE

Participants will receive JNJ-40346527 at 150 mg PO twice daily in continuous 28-day cycles. Initial response will be assessed by bone marrow biopsy after cycles 1-3 and then every 3 months thereafter. Further study assessments will be performed as outlined in the Section 7.10, Schedule of Events .

Treatment with JNJ-40346527 will continue until disease progression or stopping rules are triggered as a result of either excess toxicity or lack of efficacy (refer to Section 10.2.4).

Disease progression will be defined as any patient with response \geq PR who then loses PR based upon the original pre-treatment marrow sample (PR defined as \geq 50% decrease in marrow blasts to 5-25% of marrow). For example, a patient with 30% blasts on pre-treatment

marrow who achieved CR with 4% blasts and then was found to have 6% blasts with continued hematologic recovery on subsequent marrow (PR) would remain on trial until subsequent marrow blasts were >15%, or with loss of hematologic response. Patients with stable disease who continue to receive clinical benefit per PI review may remain on study drug.

If a participant achieves a complete remission (CR) and is deemed a candidate for allogeneic stem-cell transplant, JNJ-40346527 should be discontinued 7 days before initiation of the conditioning regimen. Treatment with JNJ-40346527 may be resumed 30-100 days after the transplant if patients has a relapse of their disease, no active GVHD, and after review by the PI.

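### The PR definition in section 8.2 has a 5% blast floor, so a fall below 5% with residual Auer rods or extramedullary disease counts as a non-response, while a smaller fall to 6% counts as a response

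*Combined protocol and SAP*

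**What the plan says.** Section 8.2 counts as an objective response anything at PR or better, "including cytogenetic and molecular responses when applicable, and will be determined at the end of each cycle". The categories that matter here are:

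- **CR and morphologic CR:** blasts under 5%, "Absence of blasts with Auer rods" and "Absence of extramedullary disease". CR also needs neutrophil and platelet recovery and freedom from red-cell transfusion.
- **CRi:** CR with only neutrophil or platelet recovery waived, so the Auer-rod and extramedullary conditions stay.
- **Cytogenetic CR:** needs morphologic CR.
- **Molecular CR:** negative molecular studies in someone whose studies were abnormal before. No morphologic condition is written.
- **PR:** "All hematologic criteria of CR", "Decrease of pretreatment bone marrow blast percentage by at least 50" percent, and "Decrease of bone marrow blast percentage to 5% to 25" percent.
- **SD:** "Not fulfilling either PR or PD criteria and clinical stability".
- **PD:** a rise in blasts of at least half.

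Section 6.3 repeats the 5% to 25% window in a parenthesis, and its worked example scores a 6% marrow with continued hematologic recovery as PR. Section 10.2.1 sets the decision rules for each arm: at least 1 response among 7 to continue, and at least 3 among 14 to call the treatment promising.

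**The concern.** A response scale should not give a worse category to a deeper reduction. PR has a floor at 5%, and every category below that floor, apart from molecular CR, also requires that Auer rods and extramedullary disease be gone. A patient who clears the blast threshold but not those conditions drops through the gap. Because SD is the residual category, the patient lands among the non-responders.

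The stake is the primary endpoint. Each arm has at most 14 patients, and one patient can decide whether it opens its second stage or is called promising. If such a patient appears and the text has not settled the category, someone must make the call after seeing the result.

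**Working it through.** **Step 1. Apply the categories literally.** Take pretreatment blasts of 30%, counts recovered, no red-cell transfusions and a clinically stable patient.

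| Blasts after treatment | Neither feature | Auer rods or extramedullary disease persists |
|---|---|---|
| 0%, 2% or 4% | CR | SD (no responding category fits) |
| 5%, 6% or 15% | PR | PR, if the hematologic criteria mean counts and transfusion only |
| 16% | SD | SD |

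The 15% limit is half of 30%. The reversal is between 4% with a residual feature (SD) and 6% (PR).

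**Step 2. Conditions on the comparison.**
- A 6% marrow is PR only with recovered counts and a fall of at least half, so pretreatment blasts must be at least 12% (6 / 0.5). From 10% or 11% to 6% is SD.
- If the patient below 5% is not clinically stable, no category applies. The patient is still not a responder.
- If the patient below 5% had an abnormal marker that is now negative, molecular CR as written would count as a response.
- If the hematologic criteria of CR are read to include Auer rods and extramedullary disease, the 6% patient with those features is not PR. The 6% patient without them still is, and the patient below 5% with them still has no responding category.

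**Step 3. Reproduce the plan's design.** Inputs from section 10.3.1 and the synopsis: rates of 5% and 30%, 80% power, one-sided 5% level. With true rate p,

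P(promising) = sum over x = 1 to 7 of Bin(x; 7, p) × P(Bin(7, p) ≥ 3 − x).

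At p = 0.30:
- x = 1: 0.2471 × 0.6706 = 0.1657
- x = 2: 0.3177 × 0.9176 = 0.2915
- x = 3 to 7: 0.3529 × 1 = 0.3529
- Total 0.810, against 80% stated.

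At p = 0.05 the total is 0.027, within the 5% level. The design reproduces.

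**Step 4. Illustrate the effect.** Let a be the share of true responders lost through the gap. The documents give no value, so a is assumed. The effective rate is 0.30 × (1 − a).

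| a (assumed) | Effective rate | Power |
|---|---|---|
| 0 | 0.300 | 81.0% |
| 2% | 0.294 | 79.8% |
| 5% | 0.285 | 77.8% |
| 10% | 0.270 | 74.1% |

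**Step 5. How often one patient is decisive.** At a true 30% rate, an arm has exactly 1 response in its first 7 with probability 7 × 0.30 × 0.70⁶ = 24.7%. It passes stage 1 and ends on exactly 3 of 14 with probability 17.6%. These are chances of standing on the edge, not chances that the gap matters. For the final rule, the chance that an arm stands on exactly 3 and at least one of the three is in the gap is 0.176 × [1 − (1 − a)³], which gives about 1.0%, 2.5% or 4.8% for a of 2%, 5% or 10%.

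**The case against.** **The patient is rare and the shares are invented.** This stands. The gap needs blasts below 5% together with a persisting feature, and Step 5 shows a small chance that it flips the final decision. The power figures show sensitivity only. A reader might infer that the design is underpowered; the documents do not support that, since the rule reproduces at 81.0% and the loss rests on an assumed share.

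**Best response protects many patients.** This also stands. Response is judged each cycle and no minimum duration is required, so a patient who has already had a qualifying PR marrow stays a responder. Only a patient whose first good marrow is already below 5%, and who never has a qualifying one, is lost.

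**Assessors may turn to the cited working-group criteria.** Section 10.2.1 refers to those criteria, but section 8.2 says its own list is amended from them, and that list is the only full set in the documents. It should be usable as written.

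**A stronger reading is tempting.** Section 6.3 calls it progression when a responder "loses PR based upon the original pre-treatment marrow sample", so a reader might infer that a PR improving from 6% to 3% with Auer rods becomes a progression and damages duration of response. The documents do not support this. The example in 6.3 treats the loss as blasts rising above half of the pretreatment value, or loss of hematologic response, and its own patient at 4% has not progressed. Section 8.2 defines PD as an increase in blasts, and section 8.2.1 counts relapse for event-free survival. A fall from 6% to 3% meets none of these.

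**Conclusion.** The gap in section 8.2 is real. Blasts below 5% with residual Auer rods or extramedullary disease fit no responding category unless molecular CR applies, while a fall of at least half to 6% with recovered counts is PR. This holds under either reading of the hematologic criteria.

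It is a minor defect in size: probably few patients, with a share that cannot be derived from the documents. It is worth repairing because the primary endpoint turns on single patients and the repair is a wording change. The conclusion concerns scoring of the primary endpoint only. It does not extend to progression or duration of response, and it does not question the two-stage design.

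**What to change.** In section 8.2, remove the 5% floor from the PR blast criterion. PR would then require a fall in marrow blasts of at least 50%, to 25% or less, in a patient not meeting CR, CRi or morphologic CR, with the count criteria kept. Blasts below 5% with residual Auer rods would then count as PR.

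In the same line, state explicitly the category for blasts below 5% with residual extramedullary disease. Whether that is a response is a judgement the sponsor should write down. Settle both points before any response is scored.

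The PR parenthesis in section 6.3 should be reconciled with the revised 8.2 definition. No change to the treatment-continuation rule is proposed here.

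The cost is an edit to one criterion in 8.2 and the cross-check in 6.3, with no new assessments. The downside is a slightly wider responder definition set against the 5% historical rate.
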